We propose to conduct a prospective randomized, and controlled study to compare the effectiveness of PROKERA® plus standard of care (SOC) in the PROKERA® Arm to SOC alone in the Control Arm. Subjects presenting with moderate DED defined as corneal fluorescein staining score of ≥ 3 points out of 9,¹⁴ will be recruited and screened at the two to three participating clinical site(s) in the United States.

Following a run-in period of 2 weeks during which enrolled subjects will use standard dry eye therapies consistent with what is described in the 2007 Report of the International Dry Eye WorkShop (DEWS)^{1,15} [e.g. preservative-free artificial tears, Restasis® (0.05% Cyclosporine A, Allergan, Inc. Irvine, CA), Xiidra® (5% lifitegrast ophthalmic solution, Shire, Lexington, MA), punctal occlusion, etc.], enrolled subjects who still present with signs and symptoms of moderate

[figure not shown]
CLINICAL STUDY PROTOCOL

DED at the screening visit, will continue in the study. Those subjects whose signs and symptoms abate during the run-in period will be discontinued from the study. Subjects who continue in the study will be assigned an appropriate study identification code, and randomized to receive either PROKERA plus SOC or SOC alone.

Subjects assigned to PROKERA plus SOC will have PROKERA inserted into one eye (study eye) and will then restart the SOC treatment for both eyes after randomization. After the PROKERA application for 5 ± 1 days together with SOC, all subjects in the PROKERA® Arm will return to the clinic to have the PROKERA removed and will continue with the SOC treatment for both eyes. Subjects assigned to the Control Arm will start the SOC treatment for both eyes after randomization and will not return to the clinic at 5-day visit. Clinical symptoms will be evaluated by OSDI scale¹⁶ and the Eye Dryness Score (EDS).^{17,18} Signs of corneal epithelial damage will be evaluated by corneal fluorescein staining at the baseline, one month, two months and three months. To assess the potential for a contralateral effect, the above evaluation will also be conducted, for the subject's fellow eye (i.e. non-study eye). In order to eliminate bias, all evaluators will be masked as to the treatment assignment.

STUDY SUBJECTS AND RANDOMIZATION:

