Subjects will first be randomized in a 1:1 ratio to either PROKERA® Arm (i.e., PROKERA plus SOC) or Control Arm (i.e., SOC only) by a computer-generated randomization code. For the PROKERA® Arm, one eye of each subject will be randomly assigned as the primary study eye.

CLINICAL STUDY PROTOCOL
STUDY FLOWCHART:

STUDY PRODUCT AND MODE OF ADMINISTRATION:

PROKERA® is manufactured by TissueTech, Inc. (Miami, FL), and is distributed by BioTissue, Inc., which is a solely owned subsidiary of TissueTech, Inc. PROKERA® is a corneal-epithelial insert, consisting of an ophthalmic conformer that incorporates cryopreserved amniotic membrane. PROKERA® is a Class II medical device that was cleared by the FDA under 510(k) #K032104 with the intended use in eyes in which the ocular surface cells have been damaged, or underlying stroma is inflamed and scarred.

Following the evaluations performed at the baseline visit, PROKERA®(Slim) will be inserted in the subject's primary study eye between the ocular surface and the eyelid as follows:

1. Apply topical anesthesia
2. Hold the upper eyelid

CLINICAL STUDY PROTOCOL

3. Ask the subject to look down
4. Insert the PROKERA® into the superior fornix
5. Pull lower eyelid down and slide PROKERA® under the lower eyelid
6. Check centration under the slit lamp
7. Apply a tape-tarsorrhaphy over the lid crease (standardized/specified in the full study protocol).

STUDY POPULATION/ DURATION:

A minimum of 50 subjects with moderate DED will be enrolled and randomized in this study. Following the baseline visit at which the subject will be randomized to either PROKERA® Arm or the Control Arm, one of the two eyes will be designated as the primary study eye. Each subject will be evaluated for a period of three months.

PARTICIPANTS' ELIGIBILITY:
Inclusion Criteria

- Subjects with moderate dry eye defined as corneal fluorescein staining score of ≥ 3
- Age ≥ 18 years
- Distance best corrected visual acuity better than 20/60 Snellen equivalent in each eye
- Willing to sign a written informed consent to participate
- Able to follow study instructions, with the intention of completing all required visits

Exclusion Criteria

- Presence of persistent corneal epithelial defect or ulcer in either eye
- Presence of active ocular infection in either eye
- Presence of ocular inflammation that is not related to keratoconjunctivitis sicca, e.g., allergy, severe blepharitis

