- Presence of other corneal disorder(s) that give rise to reduced corneal sensitivity, such as recurrent herpes keratitis
- Presence of corneal diseases other than dry eye that can disturb the pre-corneal tear film such as epithelial basement membrane dystrophy (EBMD)
- Contact lens wear
- History of recent ocular surgery/trauma, which could affect corneal sensitivity, e.g., corneal transplantation, LASIK
- Presence of cicatricial ocular surface diseases
- A medical or ocular condition, or a personal situation, which in the principal investigator's opinion, is not appropriate for participation in the trial

CLINICAL STUDY PROTOCOL

- Any scheduled or planned ocular or systemic surgery or procedure during the study
- Pregnancy and women who are expecting to be pregnant.
- Current enrolment in another interventional drug or device study or participation in such a study within 30 days of anticipated entry into this study

ENDPOINTS/ OUTCOME MEASURES:
1) EFFECTIVENESS ASSESSMENTS:
Primary Effectiveness Endpoint:

The primary effectiveness endpoint will be defined as the difference in mean change of the total corneal fluorescein staining score of the primary study eye from baseline to 1 month.

Secondary Effectiveness Endpoints

The secondary effectiveness endpoint will be defined as:

- The difference in mean change of the EDS score from baseline to 1 month.
- The difference in mean change of the OSDI score from baseline to 1 month.

Exploratory Outcomes:

- The mean changes of the corneal fluorescein staining score of the primary study eye from baseline at 2 months and 3 months.
- The mean change of the EDS score from baseline at 1 week, 2 months and 3 months.
- The mean change of the OSDI score from baseline at 1 week 2 months and 3 months.
- The same analyses at each time point for the study eye will also be conducted for the subject's fellow eye (i.e. non-study eye)

The Dry eye sign of each eye will be evaluated by the degree of corneal fluorescein staining score. The corneal fluorescein staining score is the sum of three scores by subdividing the entire cornea into upper 1/3, middle 1/3, and lower 1/3, of which each will be graded from 0 (no staining) to 3 (diffuse staining). Thus, corneal fluorescein staining score ranges from 0 to 9, with higher scores representing more severity.

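### The staining entry criterion names no eye and the PROKERA study eye is drawn at random whatever its score, so a primary study eye below 3 is not excluded

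*Combined protocol and SAP*

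**What the plan says.** - **Threshold.** Study Design describes "Subjects presenting with moderate DED defined as corneal fluorescein staining score of ≥ 3 points out of 9", and the Inclusion Criteria repeat it as "Subjects with moderate dry eye defined as corneal fluorescein staining score of ≥ 3". Neither says both eyes, at least one eye, or the study eye.
- **Neighbouring criteria do name the eye.** Acuity is "Distance best corrected visual acuity better than 20/60 Snellen equivalent in each eye", and the exclusions for epithelial defect and for infection apply to either eye.
- **Run-in check.** This is also set at subject level: "Those subjects whose signs and symptoms abate during the run-in period will be discontinued from the study". No eye and no score is given.
- **Study eye.** Study Subjects and Randomization: "For the PROKERA® Arm, one eye of each subject will be randomly assigned as the primary study eye". Study Population/Duration adds, for both arms, that after randomization "one of the two eyes will be designated as the primary study eye"; no method is stated for controls.
- **Use of that eye.** The device goes into the primary study eye, and the primary endpoint is "the difference in mean change of the total corneal fluorescein staining score of the primary study eye from baseline to 1 month".
- **Scale.** Endpoints/Outcome Measures scores each eye separately from 0 to 9.
- **Analysis.** Statistical Methods includes the study eye's baseline score as a covariate.

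**The concern.** An entry threshold on a sign score is there to ensure that the eye being analysed has measurable damage to reduce. Here the threshold is not tied to that eye. On one reading of the text, a subject scoring 5 in one eye and 1 in the other is eligible, and the random draw then takes the eye scoring 1 half the time. That eye falls short of the plan's own definition of moderate disease, yet it receives the device and contributes the primary outcome.

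What is at stake is power. The trial has 50 subjects, and eyes close to the floor of the scale pull the mean difference towards zero. Sites may also read the criterion differently, and two or three sites are planned.

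**Working it through.** **Inputs from the documents.** Scale 0 to 9, threshold 3 (Study Design, Endpoints). From Sample Size Calculation: 23 per group, two-sided 0.05, two-sample t-test, 90% power, an assumed effect size of at least 0.85, and a statement that an effect size of 1.00 corresponds to a reduction of about 35%.

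**Inputs assumed.** Share p of subjects with only one eye at 3 or more: 0% to 40%. Mean baseline of 4.5 in qualifying eyes and 1.5 in the others. Effect proportional to baseline, SD unchanged, and the same random draw in both arms.

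**Step 1: the plan's own figure.** By the exact two-sample t-test, 23 per group gives 91.2% power at effect size 1.00 and 80.5% at 0.85. Effect size 0.85 with 90% power needs 31 per group. The stated 23 therefore matches 1.00 and not 0.85. That mismatch is a separate matter, but because of it both starting points are shown below.

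**Step 2: room to improve.** An eye at 0, 1 or 2 can fall by at most 0, 1 or 2 points; a qualifying eye can fall by at least 3. At a 35% reduction the falls are 0, 0.35 and 0.70 points, against at least 0.35 × 3 = 1.05.

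**Step 3: share of study eyes below threshold.** If one eye qualifies, the draw takes the other with probability 1/2, so the share is p/2.

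**Step 4: dilution.** Mean reduction = (1 − p/2) × 0.35 × 4.5 + (p/2) × 0.35 × 1.5. Divided by the undiluted 0.35 × 4.5 = 1.575, this gives a multiplier of 1 − (p/2)(1 − 1.5/4.5) = 1 − p/3. For p = 20%: 0.9 × 1.575 + 0.1 × 0.525 = 1.470, and 1.470/1.575 = 0.933.

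**Step 5: power, 23 per group, exact t.**

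| p | study eyes below 3 | multiplier | power from 1.00 | power from 0.85 |
|---|---|---|---|---|
| 0% | 0% | 1.000 | 91% | 80% |
| 5% | 2.5% | 0.983 | 90% | 79% |
| 10% | 5% | 0.967 | 89% | 78% |
| 20% | 10% | 0.933 | 87% | 75% |
| 40% | 20% | 0.867 | 82% | 69% |

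**Sensitivity to the assumed low baseline.** If non-qualifying eyes average 2 rather than 1.5, p = 20% gives 88% from 1.00. If they gain nothing at all, the multiplier is 1 − p/2 = 0.90 and power is 85% from 1.00 and 72% from 0.85.

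**The case against.** The strongest reply is that the text is silent on the eye. It does not say that one qualifying eye is enough. An unconditional random draw makes good sense if both eyes must score at least 3, and under that reading no sub-threshold study eye arises at screening. The text also refers to a full study protocol for one procedural detail, and the flowchart is not reproduced, so a selection rule could sit there. This stands as a limit: a reader might infer that the plan expressly sets the threshold per subject, or that the trial has no such rule, and the available text supports neither. What it supports is that nothing visible excludes a study eye below 3. The run-in check does not close the gap, because it names no eye either.

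Four further points limit the concern:
- A reader might infer bias. If both arms use the same draw, the cost is dilution only. The missing control-arm rule is a separate matter.
- A reader might convert p/2 into a count of affected eyes in each arm. A random draw is stated only for the PROKERA arm, so the count can be derived for that arm alone.
- A reader might say that such eyes have no room to improve. That is true at 0. An eye at 2 still has two points, against three for an eye that only just qualifies.
- The share p could be small. At 5% the loss is about one point of power, and the documents do not rule that out.

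The baseline covariate adjusts for differences in starting score but does not restore the lost room to improve.

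**Conclusion.** The concern holds in this limited form. The criterion leaves the eye unspecified, the PROKERA-arm draw carries no condition on score, and so a primary study eye below 3 is permitted unless the sponsor meant both eyes to qualify. The consequence is a diluted primary contrast and lost power. Under the stated assumptions the loss runs from about 1 point (p = 5%) to about 9 points (p = 40%) from effect size 1.00, and from about 1 to about 12 points from 0.85. These figures illustrate scale and do not predict it: p and both baselines are assumed, and the proportional effect and constant SD are simplifications. The case for changing the plan rests on the wording gap and the low cost of closing it, not on any single row of the table.

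**What to change.** State in the Inclusion Criteria that the primary study eye must have a corneal fluorescein staining score of at least 3 at the baseline visit, after run-in. In Study Subjects and Randomization, give one selection rule for both arms: if both eyes qualify, draw the study eye at random; if only one qualifies, that eye is the study eye. If the intention was that both eyes must qualify, say that instead; the present random draw then needs no condition on score, but it should be stated for the control arm too.

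The cost is about one sentence in each section. Both eyes are already to be scored at baseline, so no procedure is added, and the study-eye rule excludes no subject who has at least one qualifying eye at that visit.

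There is one small downside. Where only one eye qualifies, the fellow eye is always the milder one, so study and fellow eyes are not exchangeable in those subjects. The exploratory fellow-eye analysis should therefore compare fellow eyes between arms, adjusted for their own baseline score.

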Safety will be assessed by documenting ADEs, in which the severity, cause and the resolution will be evaluated and reported. The Investigators will determine the severity, assign attribution, and report the event according to the Protocol guidelines. Serious ADEs such as vision threatening conditions may indicate patient withdrawal or termination of the study.

STATISTICAL METHODS:

The primary effectiveness analysis will be conducted on the primary effectiveness measure, the corneal fluorescein staining score change from baseline of the primary study eye, using a mixed-effects model of repeated measures (MMRM) for all randomized eyes within the intent-to-treat (ITT) population, with 1 month being defined as the primary effectiveness endpoint. The MMRM model will utilize Statistical Analysis System's (SAS) PROC MIXED program to perform this analysis and define treatment (PROKERA plus SOC vs. SOC) at 1 month and

CLINICAL STUDY PROTOCOL

treatment-by-month as fixed effects and subject as random effect as well as the baseline corneal fluorescein staining score of the primary study eye as the covariate. The effect of month includes 3 assessments at 1 month, 2 months, and 3 months. The comparison between PROKERA plus SOC and SOC at each month will be conducted, using a model-based t-test procedure, at the significance level of 0.05 (2-sided). The comparison between PROKERA plus SOC and SOC at 1 month will be defined as the primary effectiveness endpoint, whereas the comparisons at 2 months and 3 months will be exploratory analyses.

The OSDI total score change of the primary study eye from baseline over 3 months of the treatment assessment will be analyzed using the same MMRM model described above for the primary effectiveness measure. The comparison between PROKERA plus SOC and SOC at 1 month will be defined as the secondary effectiveness endpoint whereas the comparisons at 1 week, 2 months and 3 months will be exploratory analyses.

To assess the potential for a contralateral eye effect, the above analyses will also be conducted, the subject's fellow eye (i.e. non-study eye) as another exploratory outcome.

SAMPLE SIZE CALCULATION

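### The 1-week OSDI comparison has no matching level in the model assigned to it, and OSDI is analysed by eye although the plan describes a single total score

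*Combined protocol and SAP*

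**What the plan says.** **Time points.** The Exploratory Outcomes (under Endpoints/Outcome Measures) list "The mean change of the EDS score from baseline at 1 week, 2 months and 3 months" and "The mean change of the OSDI score from baseline at 1 week 2 months and 3 months". The 1-month changes in both scores are the secondary endpoints.

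**Model.** The Statistical Methods define a repeated-measures model for corneal staining and state its time factor: "The effect of month includes 3 assessments at 1 month, 2 months, and 3 months". OSDI is then handled by reference: it "will be analyzed using the same MMRM model described above for the primary effectiveness measure". The OSDI paragraph names the 1-month comparison as secondary, "whereas the comparisons at 1 week, 2 months and 3 months will be exploratory analyses". EDS is not mentioned in the Statistical Methods.

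**Early contact.** The Study Design describes one early visit, device removal in the PROKERA Arm: "After the PROKERA application for 5 ± 1 days together with SOC", those subjects return to the clinic. Control subjects "will not return to the clinic at 5-day visit".

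**Unit of OSDI.** The Statistical Methods describe the outcome as "The OSDI total score change of the primary study eye from baseline over 3 months" and then apply the preceding analyses to the fellow eye, to look for a contralateral effect. The fellow-eye item in the Exploratory Outcomes does the same. The description of the instrument gives 12 items, each scored 0 to 4, combined into one 0 to 100 total. It does not mention scoring by eye.

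**The concern.** There are two inconsistencies, both in how OSDI is to be analysed.

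First, the plan asks for a contrast at a time that the assigned model does not contain. The analyst would have to decide later whether to add a level, run a separate analysis, or treat the device-removal visit as the 1-week assessment. The last choice would give early symptom data in the PROKERA Arm only. If Control were contacted separately, nothing in the readable text would align the day or the setting. That matters for scores reported by subjects themselves, because the masking described in the Study Design covers the evaluators.

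Second, a contralateral effect can be sought only in an outcome measured separately in each eye. A single score per subject, analysed once as the study eye and again as the fellow eye, would show the same change twice. A reader could take that as the untreated eye improving along with the treated one.

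**Working it through.** The plan gives no figure to reproduce on this point, so the check sets its statements side by side.

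**Step 1: time levels.** OSDI time points come from the Endpoints section and the OSDI paragraph of the Statistical Methods; model levels come from the staining paragraph.

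| Time | OSDI comparison planned | Level in the assigned model |
|---|---|---|
| 1 week | yes, exploratory | no |
| 1 month | yes, secondary | yes |
| 2 months | yes, exploratory | yes |
| 3 months | yes, exploratory | yes |

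Four times are required and three are modelled: 4 − 3 = 1 missing, the 1-week level. With two arms, the model as written has 2 × 3 = 6 treatment-by-time cells, and the planned OSDI comparisons need 2 × 4 = 8. The two absent cells are the two arms at 1 week, so their difference is not a parameter of the model. A visit schedule would not change this, because it does not alter the stated time factor.

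**Step 2: where 1-week data would come from.** The removal visit falls at 5 ± 1 days, that is day 5 − 1 = 4 to day 5 + 1 = 6. Day 7 lies outside that window, and the text nowhere calls this visit the 1-week assessment. It is also attended by one arm only. The readable text gives no other early visit, window or mode of collection for either arm. In the Study Design, the sentence listing baseline and months 1, 2 and 3 concerns staining; the sentence on OSDI and EDS carries no times. The symptom schedule is therefore unstated in the readable text, which is not the same as being limited to months 1 to 3.

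**Step 3: unit of OSDI.** The stated formula is

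OSDI = (sum of item scores × 100) / (number of items answered × 4).

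With all 12 items at the maximum of 4, the sum is 12 × 4 = 48 and the score is 48 × 100 / (12 × 4) = 100. The formula has no term for the eye: one completed questionnaire gives one number. If each subject completes one questionnaire per visit, then for every subject and visit

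change labelled study eye = change labelled fellow eye.

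The outcome data in the two analyses are then the same. The fitted results could differ only through an eye-specific covariate, for example if the staining baseline of each eye were carried over literally from the staining model. Such a difference would say nothing about symptoms in the fellow eye.

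**The case against.** The strongest reply on the model is that using the same model means the same structure, fitted at OSDI's own visits. The paragraph goes on to name 1 week, and a fully literal reading would also keep the staining baseline as the OSDI covariate, which can hardly be intended. This is a fair account of the likely intention, and it makes the problem a drafting gap. It does not remove the problem: the only time factor defined has three levels, and both the fourth level and the covariate are left for the analyst to supply.

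On the unit, the Study Design says that the evaluations, including symptoms, are also made for the fellow eye, which could mean a questionnaire for each eye. The text does not exclude this, so the duplication is conditional. But nothing says that the questionnaire is given twice, and the instrument as described covers visual function and environmental triggers in one disability total.

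A reader might go further and infer that the 1-week results cannot be produced at all, or that no Control subject will have 1-week data. The documents do not support that. Control misses the 5-day clinic visit, but that visit is not equated with 1 week. EDS and OSDI are reported by the subject, so a separate or remote contact is possible. The content of the Study Flowchart is not available here and may show one. Nor do the documents state a between-arm EDS comparison at 1 week: the exploratory EDS outcome is worded as a mean change, whereas the secondary endpoints specify a difference. Since EDS is assigned no model, the three-level time factor cannot conflict with it.

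**Conclusion.** Two points hold. The exploratory 1-week comparison of OSDI cannot be estimated from the model assigned to it, which is short by one time level. This rests on the Statistical Methods alone and does not depend on the flowchart. The eye-level treatment of OSDI is inconsistent with the score as described. Assuming one questionnaire per subject per visit, the fellow-eye OSDI analysis repeats the study-eye outcome and carries no information on a contralateral effect.

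The absence of a described 1-week collection is a weaker point: it is a gap in the readable text that the flowchart may fill.

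The impact is limited. The 1-week and fellow-eye outcomes are exploratory. The primary staining endpoint is unaffected, and no sample size figure changes. The 1-month OSDI secondary endpoint is touched only in that its unit is worded as the study eye.

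**What to change.** 1. **Drop or specify 1 week.** Either delete the 1-week OSDI comparison from the Statistical Methods and the 1-week entries from the Exploratory Outcomes, or keep them and state the window and mode of collection. If kept, OSDI and EDS should be collected in both arms on the same day and by the same mode, for instance by a remote questionnaire.
2. **If kept, write out the symptom model.** Give it four post-baseline levels (1 week and months 1, 2 and 3) and name its baseline covariate. State whether EDS uses the same model. The staining model stays at three levels.
3. **Analyse OSDI once per subject.** Remove the reference to the primary study eye, and take OSDI out of the fellow-eye analyses in both sections. If a separate questionnaire per eye is really intended, say so and describe how it is administered and scored.

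Deletion costs wording only. Keeping 1 week costs at most one remote questionnaire per subject, or 50 at the planned enrolment of 50, and needs no extra clinic visit.

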score and signs such as superficial punctate keratitis (SPK) measured by fluorescein staining, leading to an overall reduction of the mean DEWS severity score from 2.9 ± 0.3 at baseline to 1.1 ± 0.3 at 1 month and 1.0 ± 0.0 at 3 months, respectively (both $p \leq 0.001$). These palliative benefits are correlated with an increase of corneal nerve density measured by *in vivo* confocal microscopy from $12,241 \pm 5,083 \mu\text{m}/\text{mm}^2$ at baseline to $16,364 \pm 3,734 \mu\text{m}/\text{mm}^2$ at 1 month, and $18,827 \pm 5,453 \mu\text{m}/\text{mm}^2$ at 3 months (both $p=0.015$). The increase of corneal nerve density is also correlated with an increase of corneal sensitivity measured by a monofilament in the Bonnet-Crochet esthesiometer. A lasting benefit for more than 3 months after one placement of PROKERA® was also demonstrated in a retrospective study by McDonald et al¹³ in 97 eyes of 84 of patients with moderate to severe DED (DEWS 2-4), of which the majority presented with symptoms of ocular discomfort, blurry vision, ocular pain, redness, and light sensitivity. Most of the cases manifested the ocular sign of SPK due to exposure keratitis, filamentary keratitis, epithelial defect, and neurotrophic keratitis. A single placement of PROKERA® for 5.4 ± 2.8 days leads to notable improvement of DED symptoms and reduction of ocular signs in 74 subjects (88%) as evidenced by notable reduction of the mean DEWS severity score from 3.25 to 1.44 at 1 week, 1.45 at 1 month, and 1.47 at 3 months. Collectively, these data suggest that a single placement of PROKERA® is effective in reducing signs and symptoms of DED for a period lasting at least three months, presumably through a number of mechanisms known for AM including anti-inflammation as well as the resultant benefit to promote the return of corneal nerve density and corneal sensitivity, which has been reported to decline as DED increases its severity.¹²

The present study is designed to further substantiate the effectiveness of PROKERA® in reducing signs and symptoms of DED.

STUDY OBJECTIVES

The primary objective is to evaluate the safety and effectiveness of PROKERA® in reducing signs and symptoms of dry eye disease (DED).

STUDY DESIGN:

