Dry eye symptoms will be evaluated using the EDS visual analog scale (VAS) to provide a direct assessment of the subject's perception of their current eye dryness symptoms. The VAS has frequently been used for the collection of patient-reported outcomes and has been

CLINICAL STUDY PROTOCOL

commonly used to assess dry eye symptoms in clinical studies. As such, the 2007 report of the International Dry Eye Workshop (DEWS) listed the VAS as a well-defined symptom assessment methodology suitable for use in dry eye clinical trials. Specifically, patient-reported outcomes assessed using the EDS (via VAS) have been used in other dry eye studies and were recently used as the primary symptom endpoint for FDA approval of lifitegrast (Xiidra) for the treatment of the signs and symptoms of dry eye disease.

The Dry eye symptoms will also be evaluated using the validated, 12-item Ocular Surface Disease Index (OSDI) (Allergan, Inc., Irvine, CA), which assesses symptoms of ocular discomfort, effects on visual function, and the impact of environmental triggers. The 12 items are graded on a scale of 0 to 4, where 0 indicates none of the time; 1, some of the time; 2, half of the time; 3, most of the time; and 4, all of the time. The total OSDI score is then calculated on the basis of the following formula: OSDI= [(sum of scores for all questions answered) \times 100]/ [(total number of questions answered) \times 4]. Thus, the OSDI is scored on a scale of 0 to 100, with higher scores representing greater disability.

2) SAFETY ASSESSMENTS:

Adverse events (AEs) during this study are expected to have the same probability of occurrence and of the same magnitude as would be found with subjects with DED and not participating in the study. These could include worsening of the signs and symptoms of dry eye. Some adverse events might be related to PROKERA® placement (adverse device effects -ADEs) which include PROKERA® intolerance, eye irritation, lid swelling and mucus discharge. However, these device related risks are no different in type or frequency when the device is used for dry eye as compared to use of the device for other ocular surface disorders which are already on-label under the FDA 510(k) clearance.

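### Safety is in the primary objective, but the only stated capture rule covers device-related events, so the visible text commits to no adverse-event count in the control arm

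*Combined protocol and SAP*

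**What the plan says.** All references are to the combined protocol and SAP.

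- **Study Objectives.** Safety and effectiveness are named together: "The primary objective is to evaluate the safety and effectiveness of PROKERA".
- **Safety Assessments, first paragraph.** Two terms are used. AEs are events in general, with worsening dry eye as the example. They "are expected to have the same probability of occurrence and of the same magnitude as would be found with subjects with DED" who are outside the study. ADEs are the device-related part: "Some adverse events might be related to PROKERA® placement (adverse device effects -ADEs". Intolerance of the device, eye irritation, lid swelling and mucus discharge are listed.
- **Safety Assessments, second paragraph.** The capture rule uses the narrower term: "Safety will be assessed by documenting ADEs, in which the severity, cause and the resolution will be evaluated and reported". It continues: "The Investigators will determine the severity, assign attribution, and report the event according to the Protocol guidelines". The sentence on serious events also uses the narrower term: "Serious ADEs such as vision threatening conditions".
- **Statistical Methods.** Staining, OSDI and fellow-eye analyses are described. There is no safety table and no summary of events by arm.
- **Study Design.** PROKERA subjects return at 5 ± 1 days for removal; control subjects have no 5-day visit. Staining is assessed in both arms at baseline and at 1, 2 and 3 months.

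**The concern.** Control subjects receive no device, so none of their events can be an ADE as the plan uses the term. If sites follow the capture rule as written, the randomized comparator contributes nothing to the safety half of the primary objective. Events in the PROKERA arm that the investigator judges unrelated to the device would also be lost, as would SOC-related events and fellow-eye events not attributed to the device.

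This matters because device effects and the disease overlap. Eye irritation is a listed ADE, yet the OSDI is a dry eye instrument "which assesses symptoms of ocular discomfort, effects on visual function, and the impact of environmental triggers". Whether discomfort during follow-up comes from the device or the disease would rest on the investigator's attribution alone, with no count from similar subjects without the device. What is at stake is a descriptive comparison. The objective does not promise a formal between-arm safety test.

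**Working it through.** The plan states no AE rate, safety sample size or safety analysis, so there is no figure to reproduce. The main check is of the text; the arithmetic only shows scale.

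**1. Which events the rule keeps.** The first paragraph of Safety Assessments makes ADEs a subset of AEs, defined by relation to PROKERA placement. The second paragraph says that safety is assessed by documenting ADEs. AEs in general appear only as an expectation, with no rule for collecting or tabulating them.

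**2. What that gives in the control arm.** Sample Size Calculation plans 50 subjects and the allocation is 1:1, so 50 / 2 = 25 per arm. With no device, the control ADE count is 0 of 25 by definition, not by observation.

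**3. What both arms do measure.** Staining, EDS and OSDI would show worsening dry eye in either arm, but they are analysed as mean changes. They do not count subjects with irritation, lid swelling, discharge or vision-threatening events.

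**4. Scale (every event count is assumed).** Suppose 8/25 = 32% of PROKERA subjects have irritation of any cause. The interval for the difference is Newcombe's, built from Wilson limits (l, u) for each arm:

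- Wilson limits: [p + z²/2n ± z√(p(1−p)/n + z²/4n²)] / (1 + z²/n), with n = 25 and z = 1.96.
- Lower limit of the difference: d − √[(p₁ − l₁)² + (u₂ − p₂)²].
- Upper limit of the difference: d + √[(u₁ − p₁)² + (p₂ − l₂)²].

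For PROKERA, 8/25 gives Wilson limits of 17.2% to 51.6%.

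| Assumed SOC count | SOC rate (Wilson 95% CI) | Excess on PROKERA (95% CI) |
|---|---|---|
| 1/25 | 4% (0.7% to 19.5%) | 28 points (6.5 to 47.9) |
| 3/25 | 12% (4.2% to 30.0%) | 20 points (−3.3 to 41.1) |
| 6/25 | 24% (11.5% to 43.4%) | 8 points (−16.4 to 31.2) |

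For the first row, the lower limit is 0.28 − √[(0.320 − 0.172)² + (0.195 − 0.040)²] = 0.065. ADE-only records would look the same in all three rows, because the SOC column would be empty.

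**5. What a two-arm table could show.** Exact power of a two-sided Fisher test at 0.05, with 25 per arm and a true 20-point difference, is 38% for 24% vs 4%, 28% for 32% vs 12%, and 23% for 40% vs 20%. The table could describe a difference but not test one reliably.

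**6. When control subjects could be asked.** Exploratory Outcomes list EDS and OSDI change at 1 week, and Statistical Methods compare the arms on OSDI at 1 week. That comparison needs control data at about day 7, although Study Design lists no 1-week assessment. The shared time points are therefore 1 week (implied) and 1, 2 and 3 months.

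**The case against.** The strongest reply is that ADE may be used loosely. The plan has cause evaluated and attribution assigned, which would be largely redundant if only events already judged device-related were written down. It also defers to protocol guidelines for reporting, and elsewhere to details "standardized/specified in the full study protocol"; the flowchart content is not shown either. Any of these could hold a rule for recording all AEs. This stands as a limit: the text supports asking for clarification and does not show that control-arm events will go unrecorded. A reader might infer that the trial collects no AEs in the control arm, but the documents do not establish that. Equally, none of the wording commits to recording AEs in both arms.

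Second, the one non-device AE that the plan names, worsening dry eye, is already followed in both arms through staining, EDS and OSDI. That is true for mean change, not for counts of the other events.

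Third, the expectation about AE probability refers to dry eye patients outside the study. A control-arm table would not test it directly, so the point should not lean on it.

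Fourth, because control subjects have no 5-day visit, a reader might infer that they would first be asked about early events at 1 month, with serious recall loss. The documents do not support this: the between-arm OSDI comparison at 1 week implies control contact soon after the wear period.

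Finally, the counts above are invented and their intervals overlap heavily. They show what cannot be seen without a control count, not how large any excess is.

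**Conclusion.** The point holds as a mismatch between the objective and the stated capture rule. Taken literally, the rule yields no control-arm safety count and drops events judged unrelated to the device. This rests on the definition of ADE in Safety Assessments and on the visible text alone; wider capture may be required elsewhere.

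The size of the loss cannot be estimated from the documents. Under the assumed counts, the same PROKERA result is compatible with an excess of anything from 8 to 28 points, depending on a control count that the rule does not collect. Even with that count, about 25 per arm gives wide intervals, so what is recovered is a descriptive background and not a test. A reader might infer that safety cannot be assessed at all or that a powered comparison is owed; the text supports neither. Device-related events would still be documented, and the objective sets no safety hypothesis. This is a cheap improvement.

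**What to change.** Replace the capture sentence in Safety Assessments with:

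> All adverse events (ocular by eye, and systemic), regardless of attribution, will be recorded in both arms from randomization to 3 months and tabulated descriptively by arm; ADEs will be reported as a subset.

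If the full study protocol already requires this, align the sentence with it.

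To make the arms comparable:

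- Ask the same AE question in both arms at every shared assessment (1 week and 1, 2 and 3 months), and record onset dates.
- State how control subjects are contacted at 1 week, since the analyses imply that assessment but Study Design does not list it.
- Show events first detected at the PROKERA-only 5-day visit separately, because an extra visit in one arm can raise that arm's count.

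The cost is one sentence, a common question at assessments already planned or implied, and slightly more data collection. The comparison will remain descriptive, with wide intervals.
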